## 9.5 Analysis Populations

### 9.5.1 Efficacy Analysis Populations

The analyses of the primary efficacy endpoints are based on the ITT population. All randomized participants will be included in this population. Participants will be analyzed in the treatment group to which they are randomized. Details on the approach to handling missing data are provided in Section 9.6.

#### Extension Study in China

**NOTE: As of Amendment 007-06, enrollment in the Extension Study in China has been stopped. This section has been updated accordingly.**

The participants in China who were randomized in the extension study will not be included in the above global study primary efficacy analysis population. The ITT participants in China, including all participants in China randomized in the global study and the extension study, will be analyzed.

### 9.5.2 Safety Analysis Populations

Safety analyses will be conducted in the APaT population, which consists of all randomized participants who received at least 1 dose of study intervention. Participants will be included in the treatment group corresponding to the study intervention they actually received for the analysis of safety data using the APaT population. This will be the treatment group to which they were randomized, except for participants who take incorrect study intervention for the entire treatment period; such participants will be included in the treatment group corresponding to the study intervention actually received. Any participant who receives the incorrect study intervention for 1 cycle, but receives the randomized treatment for all other cycles, will be analyzed according to the randomized treatment group, and a narrative will be provided for any events that occur during the cycle for which the participant is incorrectly dosed.

At least 1 laboratory, vital sign, or ECG measurement obtained after at least 1 dose of study intervention is required for inclusion in the analysis of the respective safety parameter. To assess change from baseline, a baseline measurement is also required.

#### Extension Study in China

The participants in China who were randomized and treated in the extension study will not be included in the above global study primary safety analysis population. The APaT participants in China, including all randomized participants in China (in the global study and extension study) who received at least 1 dose of study treatment, will be analyzed.

### 9.5.3 Patient-reported Outcome Analysis Population

The analyses of PRO endpoints will be based on the PRO full analysis set (FAS) population following the ITT principle and ICH E9 guidelines. The PRO FAS population consists of all

randomized participants who have received at least 1 dose of study intervention and have completed at least 1 PRO assessment.

#### **9.5.4 Pharmacokinetic Analysis Population**

The population of PK analysis set includes all the participants who have received at least 1 dose of study intervention with documented dosing history in the lenvatinib + pembrolizumab arm and have measurable plasma levels of lenvatinib or serum levels of pembrolizumab.

### **9.6 Statistical Methods**

**NOTE: As of Amendment 007-06, the prespecified interim and final analyses of the study will not be performed. Selected analyses of safety and ePRO endpoints will be performed at end of study; there will be no further analyses of efficacy endpoints. The subsections below are retained for reference.**

#### **9.6.1 Statistical Methods for Efficacy Analyses**

This section describes the statistical methods that address the primary and secondary efficacy objectives. Methods related to exploratory objectives will be described in the sSAP. Efficacy results that will be deemed to be statistically significant after consideration of the Type I error control strategy are described in Section 9.8. Nominal  $p$  values will be computed for other efficacy analyses, but should be interpreted with caution because of potential issues of multiplicity.

The stratification factors used for randomization (see Section 6.3.2) will be applied to all stratified analyses, in particular, the stratified log-rank test, stratified Cox model, and stratified Miettinen and Nurminen method [Miettinen, O. and Nurminen, M. 1985]. If there are small strata, for the purpose of analysis, strata will be combined to ensure sufficient number of participants, responses and events in each stratum. Details regarding the pooling strategy will be prespecified in the sSAP prior to the database lock for the first analysis when each applicable endpoint will be analyzed, and decisions regarding the pooling will be based on a blinded review of response and event counts by stratum.

The efficacy analyses for OR, DOR and PFS will include responses and documented progression events that occur prior to Second-course treatment.

A summary of the primary analysis strategy for the key efficacy endpoints is provided in [Table 7](#).

Table 7 Analysis Methods for Key Efficacy Endpoints

Endpoint/Variable	Statistical Method	Analysis Population	Missing Data Approach
Primary Analyses:			
PFS (RECIST 1.1) by BICR	Testing: stratified log-rank test Estimation: Stratified Cox model with Efron's tie-handling method	ITT	Censored according to rules in Table 8
OS	Testing: stratified log-rank test Estimation: Stratified Cox model with Efron's tie-handling method	ITT	Censored at last known alive date
Secondary Analyses:			
ORR (RECIST 1.1) by BICR	Testing and estimation: stratified Miettinen and Nurminen method	ITT	Participants with missing data are considered nonresponders
Abbreviations: BICR = blinded independent central review; ITT = intention-to-treat; ORR = objective response rate; OS = overall survival; PFS = progression-free survival; RECIST 1.1 = Response Evaluation Criteria in Solid Tumors.			

The strategy to address multiplicity issues with regard to multiple endpoints and interim analyses is described in Section 9.7, Interim Analyses, and in Section 9.8, Multiplicity.

#### 9.6.1.1 Progression-free Survival

The nonparametric Kaplan-Meier method will be used to estimate the PFS curve in each treatment group. The hypotheses of treatment difference in PFS will be tested by the stratified log-rank test. A stratified Cox proportional hazard model with Efron's method of tie handling will be used to estimate the magnitude of the treatment difference (ie, HR) between the treatment arms. The HR and its 95% CI from the stratified Cox model with Efron's method of tie handling and with a single treatment covariate will be reported.

Since PD is assessed periodically, PD can occur any time in the time interval between the last assessment where PD was not documented and the assessment when PD is documented. For the primary analysis, for the participants who have PD, the true date of PD will be approximated by the date of the first assessment at which PD is objectively documented per RECIST 1.1 by the BICR vendor, regardless of discontinuation of study drug. Additional analyses will be performed for PFS per iRECIST.

To evaluate the robustness of the PFS endpoint per RECIST 1.1 via BICR by the imaging vendor, 1 primary and 2 sensitivity analyses with a different set of censoring rules will be performed. For the primary analysis, if the events (PD or death) are after more than 1 missed disease assessment, the data are censored at the last disease assessment before missing visits. Also, data after new anticancer therapy are censored at the last disease assessment before the initiation of new anticancer therapy. The first sensitivity analysis follows ITT principles (ie, PDs/deaths are counted as events regardless of missed study visits or initiation of new

anticancer therapy). The second sensitivity analysis considers discontinuation of treatment or initiation of an anticancer treatment after discontinuation of study-specified treatments, whichever occurs later, to be a PD event for participants without documented PD or death. If a participant meets multiple criteria for censoring, the censoring criterion that occurs earliest will be applied. The censoring rules for primary and sensitivity analyses are summarized in Table 8.

Table 8 Censoring Rules for Primary and Sensitivity Analyses of Progression-free Survival

Situation	Primary Analysis	Sensitivity Analysis 1	Sensitivity Analysis 2
No PD and no death; new anticancer treatment is not initiated	Censored at last disease assessment	Censored at last disease assessment	Progressed at treatment discontinuation for reasons other than CR; otherwise, censored at last disease assessment if still on study intervention or completed study intervention
No PD and no death; new anticancer treatment is initiated	Censored at last disease assessment before new anticancer treatment	Censored at last disease assessment	Progressed at date of new anticancer treatment
PD or death documented after $\leq 1$ missed disease assessment and before new anticancer therapy	Progressed at date of documented PD or death	Progressed at date of documented PD or death	Progressed at date of documented PD or death
PD or death documented immediately after $\geq 2$ consecutive missed disease assessments or after new anticancer therapy	Censored at last disease assessment before the earlier date of $\geq 2$ consecutive missed disease assessment and new anticancer therapy	Progressed at date of documented PD or death	Progressed at date of documented PD or death

Abbreviation: CR = complete response; PD = progressive disease.

### 9.6.1.2 Overall Survival

The nonparametric Kaplan-Meier method will be used to estimate the survival curves. The treatment difference in survival will be assessed by the stratified log-rank test (based on the stratification factors defined in Section 6.3.2). A stratified Cox proportional hazard model with Efron's method of tie handling will be used to assess the magnitude of the treatment difference (ie, the HR). The HR and its 95% CI from the stratified Cox model with a single treatment covariate will be reported. The stratification factors used for randomization (Section 6.3.2) will be applied to both the stratified log-rank test and the stratified Cox model. Participants without documented death at the time of analysis will be censored at the date of last known contact. The analysis using the restricted mean survival time method may be conducted for OS to account for the possible nonproportional hazards effect.

### 9.6.1.3 Objective Response Rate

The stratified Miettinen and Nurminen method will be used for comparison of ORR between the treatment groups. The difference in ORR and its 95% CI from the stratified Miettinen and Nurminen method with strata weighting by sample size will be provided.

### 9.6.1.4 Duration of Response

For participants who demonstrate CR or PR, DOR is defined as the time from first documented evidence of CR or PR until PD or death due to any cause, whichever occurs first.

The nonparametric Kaplan-Meier method will be used to summarize the DOR. The median and range of DOR will be provided.

Censoring rules for DOR are summarized in [Table 9](#).

Table 9 Censoring Rules for Duration of Response

Situation	Date of Progression or Censoring	Outcome
No PD or death, no new anticancer therapy initiated	Last adequate disease assessment	Censor (nonevent)
No PD or death, new anticancer therapy initiated	Last adequate disease assessment before new anticancer therapy initiated	Censor (nonevent)
Death or PD immediately after $\geq 2$ consecutive missed disease assessments or after new anticancer therapy, if any	Earlier date of last adequate disease assessment before $\geq 2$ missed adequate disease assessments and new anticancer therapy, if any	Censor (nonevent)
Death or PD after $\leq 1$ missed disease assessments and before new anticancer therapy, if any	PD or death	End of response (event)

Abbreviation: PD = progressive disease.  
Note: A missed disease assessment includes any assessment that is not obtained or is considered inadequate for evaluation of response.

### 9.6.2 Statistical Methods for Safety Analyses

Safety and tolerability will be assessed by clinical review of all relevant parameters including AEs, laboratory tests, vital signs, and ECG measurements.

The analysis of safety results will follow a tiered approach ([Table 10](#)). The tiers differ with respect to the analyses that will be performed. AEs (specific terms as well as system organ class terms) and events that meet predefined limits of change in laboratory, vital signs, and ECG parameters are either prespecified as “Tier 1” endpoints or will be classified as

belonging to “Tier 2” or “Tier 3,” based on observed proportions of participants with an event.

### **Tier 1 Events**

Safety parameters or AEs of special interest that are identified a priori constitute “Tier 1” safety endpoints that will be subject to inferential testing for statistical significance. AEs that are immune-mediated or potentially immune-mediated are well documented and will be evaluated separately; however, these events have been characterized consistently throughout the pembrolizumab clinical development program, and determination of statistical significance is not expected to add value to the safety evaluation. Similarly, the combination of pembrolizumab and lenvatinib has not been associated with any new safety signals. Finally, there are no known AEs associated with participants with NSCLC for which determination of a *p* value is expected to impact the safety assessment. Therefore, there are no Tier 1 events for this protocol.

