### **Number of Participants:**

Global Study: Approximately 620 participants will be randomized.

Extension Study in China: Approximately 120 Chinese participants overall will be enrolled in the global study and the extension study.

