#### **Study 111/KEYNOTE-146**

Study 111/KEYNOTE-146, is a multicenter, open-label, Phase 1b/2 clinical study to evaluate the efficacy and safety of lenvatinib in combination with pembrolizumab. The primary objective of the Phase 1b portion of the study is to determine the MTD in participants with unresectable solid tumors (endometrial cancer, melanoma, NSCLC, RCC, squamous cell carcinoma of the head and neck, and urothelial cancer) who have progressed after treatment with approved therapies or for which there are no available standard effective therapies. The primary endpoint of the initial part of Phase 2 is ORR after 24 weeks of treatment, with select secondary endpoints, including OR, DCR, PFS, and duration of response (DOR).

As of the data cutoff of 01-DEC-2017, 20 participants with NSCLC were enrolled (data on file). Of the enrolled participants, 9 (45%) were PD-L1(+) (TPS  $\geq$ 1%), 5 (25%) were PD-L1(–), and 6 (30%) were not tested; 3 (15%) were treatment-naïve; and 6 (30%), 9 (45%), and 2 (10%) had 1, 2, and  $\geq$ 3 prior lines of systemic therapy, respectively. The primary endpoint of ORR at Week 24 was 30.0% (95% CI, 11.9%–54.3%). Grade 3 and 4 treatment-related AEs occurred in 11 participants (55%) and 1 participant (5%), respectively (ie, increased aspartate aminotransferase [AST]). There was 1 fatal treatment-related AE (exsanguination that was deemed possibly related to study intervention). The most common Grade 3 treatment-related AEs were hypertension (30% [6 of 20 subjects]) and fatigue, diarrhea, and hyponatremia (15% [3 of 20 subjects]). These findings indicate that the

combination of lenvatinib with pembrolizumab shows promising clinical activity with a manageable safety profile in previously treated patients with metastatic NSCLC who were not preselected for PD-L1 status.

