#### NOTE:

- The degree of proximity to major blood vessels should be considered because of the potential risk of severe hemorrhage associated with tumor shrinkage/necrosis following lenvatinib therapy.
- In the chest, major blood vessels include the main pulmonary artery, the left and right pulmonary arteries, the 4 major pulmonary veins, the superior or inferior vena cava, and the aorta.

4. Has a known history of an additional malignancy, except if the participant has undergone potentially curative therapy with no evidence of that disease recurrence for at least 3 years since initiation of that therapy.

Note: The time requirement for no evidence of disease for at least 3 years does not apply to the NSCLC for which a participant is enrolled in the study. The time requirement also does not apply to participants who underwent successful definitive resection of basal cell carcinoma of the skin, superficial bladder cancer, squamous cell carcinoma of the skin, in situ cervical cancer, or other in situ cancers.

5. Has an active autoimmune disease that has required systemic treatment in the past 2 years (ie, with the use of disease-modifying agents, corticosteroids, or immunosuppressive drugs). Replacement therapy (eg, thyroxine, insulin, or physiologic corticosteroid replacement therapy for adrenal or pituitary insufficiency, etc.) is not considered a form of systemic treatment and is allowed.
6. Has had an allogeneic tissue/solid organ transplant.

7. Has a known history of human immunodeficiency virus (HIV) infection; HIV testing is not required unless mandated by the local health authority.
8. Has a history of (noninfectious) pneumonitis that required systemic steroids or current pneumonitis/interstitial lung disease.
9. Has a known history of hepatitis B (defined as hepatitis B surface antigen [HBsAg] reactive or hepatitis B virus [HBV]-DNA detected) or known active hepatitis C virus (HCV, defined as HCV-RNA [qualitative] detected or HCV antibody reactive, if HCV-RNA is not the local SOC) infection.
  - Note: No testing for hepatitis B and hepatitis C is required unless mandated by the local health authority.
10. Has a history of a gastrointestinal condition or procedure that in the opinion of the investigator may affect oral study drug absorption.

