### **6.3 Measures to Minimize Bias: Randomization and Blinding**

#### **6.3.1 Intervention Assignment**

Intervention allocation/randomization will occur centrally using an interactive response technology (IRT) system. There are 2 study intervention arms. Participants will be assigned randomly in a 1:1 ratio to pembrolizumab + lenvatinib or pembrolizumab + matching placebo, respectively.

**NOTE: as of Amendment 007-06,** the study is unblinded. All participants remaining on treatment will receive open-label pembrolizumab monotherapy.

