### **Tier 2 Events**

Tier 2 parameters will be assessed via point estimates with 95% CIs provided for differences in the proportion of participants with events using the Miettinen and Nurminen method, an unconditional, asymptotic method [Miettinen, O. and Nurminen, M. 1985].

Membership in Tier 2 requires that at least 10% of participants in any treatment group exhibit the event; all other AEs and predefined limits of change will belong to Tier 3. The threshold of at least 10% of participants was chosen for Tier 2 events because the population randomized in this study are in critical conditions and usually experience various AEs of similar types regardless of treatment; events reported less frequently than 10% of participants would obscure the assessment of the overall safety profile and add little to the interpretation of potentially meaningful treatment differences. In addition, Grade 3 to 5 AEs ( $\geq 5\%$  of participants in one of the treatment groups) and SAEs ( $\geq 5\%$  of participants in one of the treatment groups) will be considered Tier 2 endpoints. Because many 95% CIs may be provided without adjustment for multiplicity, the CIs should be regarded as a helpful descriptive measure to be used in safety review, not a formal method for assessing the statistical significance of the between-group differences.

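### The safety plan names no lenvatinib toxicity group, so a toxicity split over several AE terms, above all haemorrhage, can end up with no grouped between-arm estimate

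*Combined protocol and SAP*

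**What the plan says.** Allocation: "Participants will be assigned randomly in a 1:1 ratio to pembrolizumab + lenvatinib or pembrolizumab + matching placebo, respectively" (Section 6.3.1). Pembrolizumab is common to both arms, so lenvatinib against placebo is the whole randomised contrast. Comparing safety between the arms is a secondary objective (Section 3).

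Section 9.6.2 sorts safety events into tiers. The units are specific AE terms, system organ class terms, and events meeting predefined limits of change in laboratory, vital-sign and ECG parameters. Nothing is placed in Tier 1. The explanation given there includes "AEs that are immune-mediated or potentially immune-mediated are well documented and will be evaluated separately" and says that "the combination of pembrolizumab and lenvatinib has not been associated with any new safety signals".

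Tier 2 gives the between-arm difference with a Miettinen-Nurminen 95% CI. The entry rule is "Membership in Tier 2 requires that at least 10% of participants in any treatment group exhibit the event", with a 5% cut-off for Grade 3 to 5 AEs and for SAEs: "of participants in one of the treatment groups) will be considered Tier 2 endpoints". Everything else is Tier 3 and receives by-arm point estimates only.

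No lenvatinib toxicity group appears in Section 9.4.2, Section 9.6.2 or Table 10. The events of clinical interest in Section 8.4.7 are the two overdose categories and a liver-test criterion.

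Elsewhere the protocol does link bleeding to lenvatinib or the combination. The note to exclusion criterion 3 (Section 5.2) cites the "potential risk of severe hemorrhage associated with tumor shrinkage/necrosis following lenvatinib therapy". The account of Study 111/KEYNOTE-146 (Section 2.2.3), covering 20 participants with NSCLC on the combination, reports: "There was 1 fatal treatment-related AE (exsanguination that was deemed possibly related to study intervention".

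**The concern.** The one family singled out belongs to the drug that does not differ between the arms. The toxicity that the randomised contrast can measure has no grouped row. Frequency tiering works term by term, so a real excess of bleeding divided among several terms may leave each of them under the cut-off. The report would then show a column of small by-arm percentages and no single difference with an interval.

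This still matters after Amendment 06. Efficacy analyses have been dropped, but selected safety analyses are still planned for the end of the study (Sections 9 and 9.6). For a combination stopped with benefit-risk judged not positive (Section 2.3), the harm that lenvatinib adds is among the main results left to report.

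**Working it through.** The plan offers no safety calculation to reproduce; its own figures here are the two cut-offs.

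**Inputs**
- Sample size: "Approximately 620 participants will be randomized" (Section 1.1), allocated 1:1, so 620 / 2 = 310 per arm. This assumes nearly everyone randomised is treated and enters the safety population.
- Cut-offs: 10% and 5% (Section 9.6.2, Table 10).
- Haemorrhage rates, the number of terms and an even split with each participant counted under one term: all assumed, and therefore shown over a range.

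**Cut-offs as counts**
- 0.10 × 310 = 31 participants.
- 0.05 × 310 = 15.5, so 16 participants.

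**Chance that split terms reach Tier 2**
Let g be the grouped rate in the lenvatinib arm, split over k terms. For one term, p = P(X ≥ 31) with X ~ Binomial(310, g/k). For any of the k terms the chance is 1 − (1 − p)^k, treating terms as independent. The grouped difference uses the expected counts, rounded, with the plan's Miettinen-Nurminen interval.

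| Grouped rates (assumed) | Terms | Rate per term | p, one term | Chance any term ≥31 | Grouped counts | Grouped difference, points (95% CI) |
|---|---|---|---|---|---|---|
| 12% vs 6% | 3 | 4.0% | 0.0004% | 0.001% | 37 vs 19 | 5.8 (1.3 to 10.5) |
| 20% vs 10% | 4 | 5.0% | 0.02% | 0.1% | 62 vs 31 | 10.0 (4.4 to 15.7) |
| 20% vs 10% | 3 | 6.7% | 1.7% | 4.9% | 62 vs 31 | 10.0 (4.4 to 15.7) |
| 25% vs 12% | 4 | 6.25% | 0.7% | 2.8% | 78 vs 37 | 13.2 (7.2 to 19.3) |
| 25% vs 12% | 3 | 8.3% | 17% | 42% | 78 vs 37 | 13.2 (7.2 to 19.3) |
| 30% vs 15% | 4 | 7.5% | 6.3% | 23% | 93 vs 46 | 15.2 (8.7 to 21.6) |

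The result turns on the rate per term. Up to about 6 to 7% per term, Tier 2 is seldom reached. At about 8% it becomes a real possibility. Every grouped interval in the table excludes zero.

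**Grade 3 to 5 or serious events**
- 8% vs 3% over three terms is 2.7% per term. P(X ≥ 16) = 1.0% per term and about 3% for any term. Grouped, 25 vs 9 gives 5.2 points (1.7 to 9.0).
- A smaller group of 15 vs 5 gives 3.2 points (0.5 to 6.4). Since 15/310 = 4.8%, even the grouped event misses the 5% cut-off, so grouping alone would not secure an estimate.

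**Where the problem does not arise**
- One dominant term with a true rate of 8%, 10% or 12% reaches 31 participants with probability 12%, 53% or 88%.
- Hypertension at the Grade 3 rate in Study 111/KEYNOTE-146 (6 of 20, 30%) would reach 16 of 310 almost with certainty, so it would get a CI.

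**The case against.** Several points on the other side have force.

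- A reader might infer that haemorrhage and similar events must fall below the cut-offs and get no between-arm estimate at all. The plan does not support this. Tiers follow observed proportions, and a dominant or common term qualifies. System organ class rows are tiered too and get a CI at 10%. Such a row covers everything in the organ system, however, so its difference is not a haemorrhage difference.
- Blood pressure, urine protein and QTc have a second route through predefined limits of change, plus by-arm summaries of continuous measures. That narrows the gap mainly to haemorrhage.
- A reader might infer that the protocol treats all its cardiovascular, proteinuria, QTc, LVEF and fistula exclusions as lenvatinib risks. Those criteria do not name lenvatinib as the cause; the vessel-invasion note does. Sections 8.3.2 and 8.3.3 link extra blood pressure and ECG measurements to lenvatinib, but those measurements have the limit-based route.
- A reader might infer that the statement about no new signals is the reason lenvatinib toxicity is left ungrouped. In context it only explains why nothing gets a p value. Nor does separate evaluation promise a between-arm estimate for immune-mediated events.
- The supplemental SAP is not available here, Section 9.6 is now kept for reference, and the safety analyses to be performed are only described as selected. A haemorrhage group could exist there. This stands as a condition on the point. Against it, Section 9.1 calls Sections 9.2 to 9.12 the comprehensive plan, and they neither contain nor cite such a group.
- The study is unblinded, so a group added now cannot carry full prespecification. That calls for disclosure, and does not favour leaving the estimate out.

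**Conclusion.** The point holds in a limited form. As written, Section 9.6.2 can leave haemorrhage, a risk the protocol itself connects with lenvatinib, without a grouped difference and interval, while the only family set apart is tied to the drug given in both arms. It is a risk and not a certainty. Under even splits at roughly 4 to 7% per term, the chance that any term reaches Tier 2 is about 5% or less, against grouped differences of 5.8 to 13.2 points whose intervals exclude zero. At about 7.5 to 8.3% per term the chance rises to 23 to 42%, and with one dominant term Tier 2 may be more likely than not.

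These sizes rest on assumed rates, an even split without overlap, and about 310 treated per arm. The conclusion also assumes that the supplemental SAP holds no such group. By-arm percentages would be shown in any case, so what is missing is the grouped comparison.

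**What to change.** In Section 9.6.2 and Table 10, add a haemorrhage group and any other lenvatinib-associated groups already on the programme's list. Report each whatever its frequency, for any grade, Grade 3 to 5, serious and fatal events, with the risk difference and Miettinen-Nurminen 95% CI and no p value. Exempting the groups from the frequency rule matters, as the 15 vs 5 example shows.

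Take the terms from existing standard lists, chosen without reference to by-arm counts, and state in the clinical study report that the addition was made after unblinding. If the supplemental SAP already defines such groups, a cross-reference from Section 9.6.2 is enough. The sentence about no new signals can stay.

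The cost is some SAP wording and a few tables from data already collected. The downside is a few more descriptive intervals without multiplicity adjustment, which the Tier 2 text already accepts.
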